## 8.5. Genetics

A 6 mL blood sample for DNA isolation will be collected from participants who have consented to participate in the genetics analysis component of the study. Participation is optional. Participants who do not wish to participate in the genetic research may still participate in the study.

In the event of DNA extraction failure, a replacement genetic blood sample may be requested from the participant. Signed informed consent will be required to obtain a replacement sample unless it was included in the original consent.

Details on processes for collection and shipment and destruction of genetic research samples can be found in the SRM.

## 8.6. Patient Reported Outcomes

Patient Reported Outcomes assessments will be conducted according to the SoA.

CCI

A large black rectangular redaction box covers the majority of the page below the CCI label, starting below the text and ending above the additional information statement.

Additional information will be provided in SRM.

## 9. PHARMACOKINETIC METHOD OF ANALYSES

The department of Clinical Pharmacology Modelling & Simulation (CPMS) will be responsible for the PK data analysis of the CAB and RPV data.

PK analysis of the plasma CAB and RPV concentration-time data will be conducted using non-compartmental methods with WinNonlin (Version 6.3 or higher). Actual sampling and dosing times as recorded in eCRF will be used for analysis. From the plasma concentration-

time data, the following pharmacokinetic parameters will be determined, as data permit: AUC(0-∞), AUC(0-t), Cmax, tmax, half-life (t1/2), and absorption rate constant (KALA).

Plasma CAB and RPV concentration data will be presented in graphical and/or tabular form and will be descriptively summarized.

Details of PK analyses will be provided in the report and analysis plan (RAP) separately.

## **10. STATISTICAL CONSIDERATIONS**

### **10.1. Statistical Hypotheses**

The primary objective of this study is to evaluate the pharmacokinetics of CAB and RPV following a single intramuscular administration of each in the lateral thigh of healthy adult participants. No formal statistical hypotheses are to be tested. Where appropriate, an estimation approach will be taken and point estimates and confidence intervals will be constructed.

### **10.2. Sample Size Determination**

There was no formal calculation of power or sample size for this study. Approximately 15 participants will receive CAB LA + RPV LA IM injections and provide informative safety and pharmacokinetic data based on feasibility considerations.

### **10.3. Populations for Analyses**

The following populations are defined:

Population	Description
Enrolled	All participants who sign the ICF.
Safety	All participants who take at least 1 dose of study drug.
Pharmacokinetic Concentration	All participants who undergo plasma PK sampling and have evaluable PK assay results. This population will be used for the concentration listing.
Pharmacokinetic Parameter	All participants who undergo plasma PK sampling and have evaluable PK parameters estimated. This population will be used for PK parameter listing, plotting of the concentration-time data and PK parameter summary.

### **10.4. Statistical Analyses**

The statistical analysis plan will be finalized prior to Database Release (DBR) and it will include a more technical and detailed description of the statistical analyses described in

this section. This section is a summary of the planned statistical analyses of the most important endpoints including primary and key secondary endpoints.

#### **10.4.1. General Considerations**

Final analysis will be performed after the completion of the study and final datasets authorization. Data will be listed and summarized according to GSK reporting standards, where applicable.

Unless stated otherwise, descriptive summaries will include n, mean, standard deviation (SD), median, minimum, and maximum for continuous variables, whereas n and percent will be used as summary statistics for categorical variables. For PK data, coefficient of variation (%CV), geometric mean with associated 95% confidence interval (CI), and the between- participant CV (%CVb) for the log-transformed PK parameters will also be provided as appropriate.

Baseline or pre-dose assessment is the last available assessment prior to time of the first dose unless it is specified otherwise. If there are multiple assessments collected on the same scheduled time, the average of these assessments will be used. For tabulated safety summaries, only the scheduled assessments will be included in the summary tables.

Version 9.4 or higher of the SAS system will be used to analyze the data as well as to generate tables, figures, and listings. Complete details will be documented in the RAP.

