## 11.2. Appendix 2: Assessment Windows

All assessments/events (including those from planned, unscheduled and withdrawal visits) will be assigned to assessment windows/analysis visits according to actual dates of collection rather than the nominal visit labels recorded on the eCRF or in the laboratory database. All assessment data, including unscheduled data will be presented in listings.

For parameters which are not scheduled to be assessed at a particular visit, the all-inclusive assessment windows will still be used; however, data displays summarizing measurements by visit will only report visits in which the parameter is a planned collection according to [Appendix 1: Schedule of Activities](#)

Note: Prior to visit slotting, assessments are first assigned to a study phase according to [Table 3](#).

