
 
Unscheduled visits will be assigned to a study visit using assessment windows defined in Section 11.2.1.
 
However, data summaries will only report visits that are planned assessment time points for each parameter (according to the Schedule of Activities in Section 11.1).
 
Evaluatable assessments at unscheduled visits will be used when categorizing values across visits, such as 'maximum grade during the injection phase'.
 
	
Descriptive Summary Statistics	
Continuous Data	Refer to GSK Standard Statistical Display Principle 6.06.1
Categorical Data	N, n, frequency, %
Graphical Displays	

 
Refer to GSK Standard Statistical Display Principles 7.01 to 7.13.
 
	

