## 11.5. Appendix 5: Derived and Transformed Data

### 11.5.1. General

Multiple Measurements at One Analysis Time Point

 
If there are multiple measurements within a time window (per Section 11.2.1), the value closest to the target day for that window will be used. If values are the same distance from the target, then the mean of the measurements (for quantitative parameters including ECG values) or the worst-case of the measurements (for qualitative parameters) will be calculated and used in any derivation of summary statistics.
 
Only planned assessment timepoints (according to Appendix 2: Schedule of Activities) will be included in data displays summarizing measurements by visit.
 
Assessments not chosen for use in summary statistics will still appear in the associated listings.
 
All applicable valid assessments, irrespective of proximity to the target study day, will be used when categorizing values across visits, such as 'maximum grade during the intervention phase' or 'at any time post-baseline', and for any algorithm that has specific rules for which observation to use (e.g. LOCF).
 

Change from Baseline

 
Post-Dose Visit Value – Baseline
 
Unless otherwise specified, the baseline definitions specified in Section 6.2 will be used for derivations for endpoints / parameters.
 

Study Day

 
The Study Day of an event (e.g., lab assessment, vital sign, ECG, start date of AE) will be derived as the number of days between the date of the event and the Intervention Phase treatment start date as follows: 
 
If date of event <math>\geq</math> start date of study treatment, then 
 
Study Day = Date of Event - Intervention Phase Treatment Start Date +1
 
 
 
If date of event <math><</math> start date of study treatment, then 
 
Study Day = Date of Event - Intervention Phase Treatment Start Date
 
 
 
Note that the start date of each phase is on Study Day 1 and the day before this is Study Day -1; i.e., there is no Study Day 0.
 
 
 

Phase Day

 
Calculated as the number of days from First Dose Date of CAB + RPV for the respective phase (based on study period classifications in Table 3):
 

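### By-visit safety tables: the protocol admits scheduled assessments only, but the SAP lets an unscheduled value replace or be averaged with the scheduled one, and does not declare the change

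*Protocol*

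**What the plan says.** Protocol 10.4.1 (General Considerations) sets the rule without exception: "For tabulated safety summaries, only the scheduled assessments will be included in the summary tables". The same section closes by leaving detail to the analysis plan: "Complete details will be documented in the RAP".

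The SAP has four relevant rules.

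- **Slotting.** Section 11.2: "All assessments/events (including those from planned, unscheduled and withdrawal visits) will be assigned to assessment windows/analysis visits according to actual dates of collection". Section 11.4.2 repeats it: "Unscheduled visits will be assigned to a study visit using assessment windows defined in Section 11.2.1".
- **Selection within a window.** Section 11.5.1: with several measurements, "the value closest to the target day for that window will be used". For quantitative ties: "If values are the same distance from the target, then the mean of the measurements" is used. Neither sentence distinguishes scheduled from unscheduled samples.
- **What is displayed.** Section 11.5.1: "Only planned assessment timepoints (according to Appendix 2: Schedule of Activities) will be included in data displays summarizing measurements by visit".
- **Across-visit categories.** Section 11.4.2: "Evaluatable assessments at unscheduled visits will be used when categorizing values across visits, such as 'maximum grade during the injection phase". Section 11.5.1 says the same of all valid assessments.

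SAP 2.1 and Table 1 declare four changes from the protocol: Covid-19 displays, PK parameters for the oral lead-in, the questionnaire version, and listings for all screened subjects. The use of unscheduled data is not among them.

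**The concern.** Two programmers, one following the protocol and one following the SAP, could fill the same cell of a by-visit table with different samples. The tables concerned are chemistry (3.25, 3.26), hematology (3.28, 3.29), ECG values (3.34, 3.35) and vital signs (3.37).

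The choice is not neutral. Protocol 8.1.4 asks for clinically significant abnormal laboratory values to be repeated, and Appendix 6 sets repeats within 24 hours, or 24 to 72 hours, once ALT reaches 3 times the upper limit of normal. Whether an unscheduled value exists therefore depends on what the scheduled one showed. With about 15 injected participants, one substitution can visibly change a visit mean. Safety and tolerability is a stated study objective, so its tables should rest on one declared rule.

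**Working it through.** The plan states no figure on this point, so the check applies both rules to the SAP's own windows.

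**Inputs from SAP Table 9 (Injection Phase).** Day 8 laboratory window: Days 2 to 10, target 8. Week 4 laboratory window: from Day 24, target 28. Day 15 vital-sign window: Days 12 to 16, target 14. Number injected: about 15 (protocol 10.2).

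**Rule.** Let s be the day of the scheduled sample, u the day of the unscheduled one and t the target. The protocol always uses the sample from day s. The SAP uses the unscheduled sample if |u − t| < |s − t|, the mean of the two if these distances are equal, and the scheduled sample otherwise.

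| Window | s | u | Distances, scheduled / unscheduled | SAP result |
|---|---|---|---|---|
| Labs, Day 8 | 8 | 8 | 0 / 0 | averaged |
| Labs, Day 8 | 8 | 6 | 0 / 2 | scheduled kept |
| Labs, Day 8 | 7 | 8 | 1 / 0 | replaced |
| Labs, Day 8 | 7 | 9 | 1 / 1 | averaged |
| Labs, Day 8 | 7 | 10 | 1 / 2 | scheduled kept |
| Labs, Week 4 | 29 | 28 | 1 / 0 | replaced |
| Labs, Week 4 | 29 | 27 | 1 / 1 | averaged |
| Vital signs, Day 15 | 15 | 14 | 1 / 0 | replaced |
| Vital signs, Day 15 | 15 | 13 | 1 / 1 | averaged |

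Three things follow.

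- Phase day is counted in whole days, so a same-day repeat always ties and is averaged.
- A sample exactly on target is never displaced by one from another day.
- At the Day 15 vital-sign timepoint, a reading taken exactly on schedule is already one day off the SAP's target, so it can be displaced with no deviation at the site.

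**Size, with assumed ALT values.** Suppose 14 participants have 25 U/L and one has a scheduled value of 160.

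- Protocol rule: (14 × 25 + 160)/15 = 34.0.
- Replaced by a repeat of 60: (14 × 25 + 60)/15 = 27.3, which is 20% lower.
- Averaged with that repeat, (160 + 60)/2 = 110: (14 × 25 + 110)/15 = 30.7, which is 10% lower.
- Replaced by a repeat of 140: (14 × 25 + 140)/15 = 32.7, which is 4% lower.
- Opposite direction, a scheduled 30 replaced by an unscheduled 120: the mean rises by (120 − 30)/15 = 6.0. If averaged to 75, it rises by (75 − 30)/15 = 3.0.

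In the first four cases the visit median stays at 25.

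**The case against.** **The SAP can be read as agreeing with the protocol.** It limits by-visit displays to planned timepoints, says unscheduled readings appear in listings (11.4.2), and speaks of planned data for withdrawn participants (11.6.1). This has some force, because the text could be clearer. But the limit in 11.2 concerns visits at which the parameter is a planned collection. It settles which visits are shown, not which sample fills them, and both 11.2 and 11.4.2 expressly put unscheduled assessments into those visits.

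**The protocol leaves detail to the analysis plan.** It does, but reversing an explicit sentence is a change, and the SAP has a table for declaring changes.

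**The protocol itself averages multiple readings.** Section 10.4.1 does so for readings at the same scheduled time, in the paragraph on baseline. That naturally covers replicates such as triplicate ECGs. It does not clearly reach an unscheduled repeat later the same day.

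**By-visit tables are biased towards recovery.** A reader might infer this. The documents do not support it as a general statement. A later-day repeat displaces the scheduled value only if the scheduled sample preceded the target and the repeat lies nearer to it. An unscheduled abnormal value before a late scheduled visit shifts the mean the other way. A Day 7 laboratory draw is also an assumption: the schedule labels the visit Day 7/8, while the SAP's laboratory target is Day 8.

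**Worst-grade tables would miss unscheduled peaks.** A reader might infer this too. The protocol (10.4.3) plans laboratory, vital-sign and ECG summaries by visit and plans maximum grade only for adverse events. The laboratory maximum-grade tables (3.27, 3.30) come from the SAP and already count every valid value, so no such peak is lost.

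**Nearest-to-target is a coherent prespecified rule.** True, but it is not the protocol's rule, and it admits repeats triggered by the result.

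**Conclusion.** The contradiction is real and undeclared. Its effect on results is conditional: by-visit values *can* differ between the two documents, and do so only if an unscheduled value falls in the window and is nearer to the target or tied with it. The SAP's Day 14 target for the Day 15 vital-sign timepoint makes this possible even for an on-schedule reading.

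In the illustrative cases, one participant moves a visit mean ALT by 4% to 20%. The ALT values are assumptions, and so is the Day 7 draw where it is used. The selection depends on outcome; the shift is often towards recovery but is not certain to be.

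The SAP's use of all values for maximum grade is sensible, though it too departs from the protocol sentence and should be declared. The nearest-value rule does not affect listings, the liver tables (3.32, 3.33) or the primary PK endpoints, and a scheduled peak displaced from a visit mean still counts towards maximum grade. This should be corrected, but it does not threaten the study's main conclusions.

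**What to change.** 1. In SAP 11.5.1, state that by-visit values and changes from baseline use the scheduled (nominal visit) assessment when it exists, and an unscheduled value only when the scheduled one is missing. The baseline definition in SAP 5.2 can stay as it is.
2. In SAP Table 9, correct the target for the Day 15 vital-sign timepoint, now given as 14. The PK row for Day 15 carries the same target; its window is a single day, so nothing changes there, but it should be aligned.
3. Keep the SAP's rule that maximum-grade and liver-criteria tables use all post-baseline values, scheduled or not.
4. In SAP Table 1, list two departures from protocol 10.4.1: the all-values rule for those tables, and the use of an unscheduled value when the scheduled one is missing.

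The cost is a few lines of SAP text and one selection rule in the laboratory, vital-sign and ECG datasets. No new data and no protocol amendment are needed. The SAP is a critical-components version whose list of displays is still tentative (Appendix 9), so the change can be made when the full plan is written.

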#### **10.4.2. Primary Endpoint(s)**

Descriptive statistics and/or graphics will be created to describe the primary endpoints of interest. Concentrations will be determined directly from concentration-time data from each matrix. Data will be presented in tabular and or graphical format and summarized descriptively according to GSK's Integrated Data Standards Library (IDSL) standards. No formal statistical testing will be conducted.

Pharmacokinetic analyses will be the responsibility of Clinical Pharmacokinetics Modeling & Simulation Department within GSK. Plasma CAB and RPV concentration-time data will be analyzed by non-compartmental methods with WinNonlin Professional 5.2 or higher, Phoenix (Pharsight Corporation) or comparable software. Calculations will be based on the actual sampling times recorded during the study.

The following pharmacokinetic parameters will be determined, as data permits, for the PK profile of CAB LA + RPV LA:

- maximum observed concentration (Cmax)
- time of maximum observed concentration (tmax)
- area under the concentration-time curve from time zero to last quantifiable time point (AUC(0-t))
- area under the concentration-time curve from time zero to infinity (AUC(0-∞))
- apparent terminal phase half-life (t1/2)
- absorption rate constant (KALA)

#### **10.4.3. Secondary and Safety Endpoint(s)**

All secondary and safety analyses will be performed on the Safety Population. AEs will be summarized using MedDRA preferred terms. All AEs, drug-related AEs, SAEs, liver-related AEs and AEs leading to permanent discontinuation of study drug or withdrawal will be summarized or listed. AEs and drug-related AEs will also be summarized by maximum toxicity grade (based on DAIDS categories). Laboratory data, vital signs and ECG data (absolute values and change from Baseline) will be summarized by visit. Liver chemistry abnormalities will be summarized or listed. Details will be documented in the RAP.

#### **10.5. Interim Analyses**

There is no planned formal interim analysis. All preliminary safety, tolerability and available pharmacokinetic data may be reviewed internally at any time point. Depending on feasibility, evaluation of PK data may be performed at time points such as Week 4 and Week 12 post injection for preparatory PK modelling.

## **11. SUPPORTING DOCUMENTATION AND OPERATIONAL CONSIDERATIONS**

### **11.1. Appendix 1: Regulatory, Ethical, and Study Oversight Considerations**

#### **11.1.1. Regulatory and Ethical Considerations**

- This study will be conducted in accordance with the protocol and with:
  - Consensus of ethical principles derived from international guidelines including the Declaration of Helsinki and Council for International Organizations of Medical Sciences (CIOMS) International Ethical Guidelines
  - Applicable ICH Good Clinical Practice (GCP) Guidelines
  - Applicable laws and regulations
- The protocol, protocol amendments, ICF, Investigator Brochure, and other relevant documents (e.g., advertisements) must be submitted to an IRB/IEC by the investigator and reviewed and approved by the IRB/IEC before the study is initiated.
- Any amendments to the protocol will require IEC/IRB approval before implementation of changes made to the study design, except for changes necessary to eliminate an immediate hazard to study participants.
- The investigator will be responsible for the following:
  - Providing written summaries of the status of the study to the IRB/IEC annually or more frequently in accordance with the requirements, policies, and procedures established by the IRB/EC
  - Notifying the IRB/IEC of SAE or other significant safety findings as required by IRB/IEC procedures

Providing oversight of the conduct of the study at the site and adherence to requirements of 21 CFR, ICH guidelines, the IRB/IEC, European regulation 536/2014 for clinical studies (if applicable), and all other applicable local regulations.

#### **11.1.2. Financial Disclosure**

Investigators and sub-investigators will provide the sponsor with sufficient, accurate financial information as requested to allow the sponsor to submit complete and accurate financial certification or disclosure statements to the appropriate regulatory authorities. Investigators are responsible for providing information on financial interests during the course of the study and for 1 year after completion of the study.

#### **11.1.3. Informed Consent Process**

- The investigator or his/her representative will explain the nature of the study to the participant and answer all questions regarding the study.

- Participants must be informed that their participation is voluntary. Participants or their legally authorized representative will be required to sign a statement of informed consent that meets the requirements of 21 CFR 50, local regulations, ICH guidelines, Health Insurance Portability and Accountability Act (HIPAA) requirements, where applicable, and the IRB/IEC or study center.
- The medical record must include a statement that written informed consent was obtained before the participant was enrolled in the study and the date the written consent was obtained. The authorized person obtaining the informed consent must also sign the ICF.
- Participants must be re-consented to the most current version of the ICF(s) during their participation in the study.
- A copy of the ICF(s) must be provided to the participant or the participant's legally authorized representative.

Participants who are rescreened are required to sign a new ICF.

GSK/ViiV (alone or working with others) may use participant's coded study data and samples and other information to carry out this study; understand the results of this study; learn more about the study intervention and the injection site; publish the results of these research efforts; work with government agencies or insurers to have the study intervention approved for medical use or approved for payment coverage.

#### **11.1.4. Data Protection**

- Participants will be assigned a unique identifier by the sponsor. Any participant records or datasets that are transferred to the sponsor will contain the identifier only; participant names or any information which would make the participant identifiable will not be transferred.
- The participant must be informed that his/her personal study-related data will be used by the sponsor in accordance with local data protection law. The level of disclosure must also be explained to the participant who will be required to give consent for their data to be used as described in the informed consent.
- The participant must be informed that his/her medical records may be examined by Clinical Quality Assurance auditors or other authorized personnel appointed by the sponsor, by appropriate IRB/IEC members, and by inspectors from regulatory authorities.

